### 6.2 Descriptive, Exploratory Analyses

Categorical variables will be displayed by absolute and relative frequencies (percentages). Percentages for categorical variables will be based on all non-missing values (=100%). Percentages will be rounded to one decimal place and therefore, there may be occasions when the total of the percentages does not exactly equal 100%.

Continuous variables will be summarised with number of observations, mean, standard deviation, median, minimum, maximum and the 5%, 25%, 75% and 95% quantiles. These descriptive statistics will be calculated for absolute values and for absolute differences to baseline, where appropriate.

### 6.3 Subgroup analyses

The primary endpoint will be conducted also by subgroups. The following subgroups will be considered:

- Baseline IGA (3, 4)

Further subgroups may be defined in the BDRM protocol if reasonable.

## 7 Final analysis

The following chapter summarises all analyses planned for the analysis of data collected within this trial.

### 7.1 Demographic and other baseline characteristics

Analyses of demographic will be performed as described in chapter 6.2 with the Randomised Set, details of the used analysis sets are described in chapter 8. The analysis will only be displayed overall. The following variables will be analysed:

- Age at time of consent [years]
- Gender (male, female)
- Height [cm]
- Weight [kg]
- BMI [kg/m^2]
- Race (American Indian or Alaska Native, Asian, Black or African American, Native Hawaiian or Other Pacific Islander, White, Other)
- Ethnicity (Hispanic or Latino, Not Hispanic or Latino)

Demographic data will be listed.

The incidence of previous and concomitant diseases (“Medical History”) will be displayed by MedDRA primary System Organ Class (SOC) and Preferred Term for the FAS.

### 7.2 Efficacy - Primary Endpoint Evaluation

Descriptive statistics will be provided for the two primary endpoints separately with the FAS.

Both primary efficacy endpoints will be analysed as defined in chapter 6.1 with the FAS.

These analyses will be displayed not only overall but also by subgroups as defined in chapter 6.3. The overall analysis will be repeated in an exploratory sense with the PPS.

### 7.3 Efficacy - Secondary Endpoints Evaluation

All secondary efficacy analyses will be performed as described in chapter 6.2 with the FAS only.

IGA and EASI-75 responders at other time points will also be analysed using a GLMM model similar to that described in Section 6.1.

The efficacy variables and their changes from baseline will be summarized with descriptive statistics per treatment group and visit. This applies to the vIGA-ADTM, EASI, NRS scores for

pruritus, DLQI, POEM, SCORAD, AIS and PO-SCORAD. Change from baseline endpoints will be analysed using Mixed Model with Repeated Measures (MMRM) with Treatment Arm, Visit and Treatment x Visit Interaction as a factors and baseline value as a covariate, to account for missing data. For vIGA-ADTM as a 5-level ordinal variable, mixed ordinal logistic regression will be used with factors defined as above and IGA at baseline as a factor too.

If rescue medication is used, the patient will be specified as a non-responder from the time the rescue is used.

The following parameters will be analysed as described above:

- Proportion of patients achieving a vIGA-ADTM score of 0 (clear) or 1 (almost clear) and a decrease of at least 2 points in vIGA-ADTM in treated population compared to placebo population from baseline to Week 4, 8, 12, 18 and 20
- Change in proportion of patients achieving a vIGA-ADTM score of 0 (clear) or 1 (almost clear) and a decrease of at least 2 points in vIGA-ADTM in treated population compared to placebo population from Week 16 to Week 18 and 20.
- Absolute proportion of patients achieving EASI-75 ( $\geq 75\%$  improvement from baseline) in treated population compared to placebo population at Week 4, 8, 12, 18 and 20
- Change from baseline in vIGA-ADTM score in treated population compared to placebo population to Week 4, 8, 12, 16, 18 and 20
- Change from Week 16 in vIGA-ADTM score in treated population compared to placebo population to Week 18 and 20.
- Change from baseline in EASI in treated population compared to placebo population to Week 4, 8, 12, 16, 18 and 20
- Change from Week 16 in EASI in treated population compared to placebo population to Week 18 and 20.
- Absolute proportion of patients achieving a decrease of at least 4 points in worst itch NRS in treated population compared to placebo population from baseline to Week 4, 8, 12, 16, 18 and 20. The NRS endpoint should be recorded weekly (descriptive values), as defined in section 4.2.6 and p-values only provided for the weeks defined in the endpoint.
- Absolute proportion of patients achieving a decrease of at least 3 points in worst itch NRS in treated population compared to placebo population from baseline to Week 4, 8, 12, 16, 18 and 20. The NRS endpoint should be recorded weekly (descriptive values), as defined in section 4.2.6 and p-values only provided for the weeks defined in the endpoint.
- Change from baseline in worst itch NRS in treated population compared to placebo population to Week 4, 8, 12, 16, 18 and 20. The NRS endpoint should be recorded weekly (descriptive values), as defined in section 4.2.6 and p-values only provided for the weeks defined in the endpoint.
- Change from Week 16 in worst itch NRS in treated population compared to placebo population to Week 18 and 20. The NRS endpoint should be recorded weekly (descriptive values), as defined in section 4.2.6 and p-values only provided for the weeks defined in the endpoint.
- Absolute proportion of patients achieving EASI-50 ( $\geq 50\%$  improvement from baseline) in treated population compared to placebo population at Week 4, 8, 12, 16, 18 and 20.

- Change from baseline in the Body Surface Area (BSA) affected by AD in treated population compared to placebo population to Week 4, 8, 12, 16, 18 and 20.
- Change from Week 16 in the Body Surface Area (BSA) affected by AD in treated population compared to placebo population to Week 18 and 20.
- Change from baseline in the SCORing Atopic Dermatitis (SCORAD) score in treated population compared to placebo population to Week 4, 8, 12, 16, 18 and 20.
- Change from Week 16 in the SCORing Atopic Dermatitis (SCORAD) score in treated population compared to placebo population to Week 18 and 20.

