	
For the purpose of efficacy analysis, patients who receive rescue treatment during the study treatment period will be considered treatment failures from the time rescue treatment is used.
 
Topical corticosteroids or calcineurin inhibitors may be used for rescue, but should be reserved for problem areas only, eg, face, neck, intertriginous and genital areas, etc. If a patient receives rescue treatment with systemic corticosteroids or non-steroidal systemic immunosuppressive drugs (cyclosporine, methotrexate, mycophenolate mofetil, azathioprine, etc.) study treatment will be immediately discontinued.
 
Investigators should make every attempt to conduct efficacy and safety assessments (eg, disease severity scores, safety labs) immediately before administering any rescue treatment.

STATISTICAL ANALYSIS	
The primary analysis will be conducted in the full analysis set (FAS) population.
 
A longitudinal mixed model for binary outcomes (GENMOD) will be used to separately analyze the binary primary and secondary efficacy endpoints at Week 16.
 
Change from baseline for secondary and exploratory endpoints (vIGA-ADTM, EASI, NRS, BSA, SCORAD, DLQI, POEM, AIS and PO-SCORAD) will be analysed using mixed model with repeated measures (MMRM). The models will include Treatment Arm as a factor and respective baseline value as a covariate, with the treatment-by-visit interaction term as a random effect to account for missing data at Week 16.
 
Sensitivity analyses will be performed to assess the robustness of the Missing at Random (MAR) assumptions that support the GENMOD methods above for imputing missing data.

SPONSOR:	DS Biopharma

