### **DS107 Capsules Phase 2b Study (DS107G-03)**

This was a randomised, double-blind, placebo-controlled, Phase 2b study to assess the efficacy and safety of 1g or 2g DS107 administered orally once daily versus placebo administered orally once daily in adult patients with moderate to severe AD. The primary efficacy endpoint was defined as the proportion of patients achieving an IGA of 0 (clear) or 1 (almost clear) and a decrease of at least two points in IGA at Week 8. Secondary and exploratory efficacy variables included IGA measurements, pruritus (obtained from the NRS), EASI, BSA, POEM, DLQI, Patient Global Impression of Severity (PGI-S) score and Patient Global Impression of Change (PGI-C) score.

When the data was analyzed by baseline AD severity, a clear trend towards a dose-dependent IGA response was observed in the severe sub-group ( $n=45$ ). At Week 8, there was a dose-dependent IGA response; more patients in the DS107 treatment groups (2g DS107 – 41.7%, 1g DS107 – 37.5%) than the placebo treated group (25.0%) achieved treatment success.

The trend of improvement displayed no evidence of treatment plateau, suggesting that greater clinically meaningful improvements from baseline could be expected with a larger sample size or if treatment were to be continued for a longer time period. 2g DS107 (50.0%) and 1g DS107 (50.0%) demonstrated a trend towards sustained superiority in IGA response over placebo (33.3%) at Week 10 (Follow-up).

Although most scores and indexes achieved clinically meaningful improvements at Week 8, with improvements at each time point during the study, no statistically significant differences among the treatment groups were observed, with notably high placebo responses across multiple endpoints.

Similar to the primary endpoint, a clear trend towards a dose-dependent improvement in pruritus NRS is observed in the severe sub-group. At Week 8, there was a dose-dependent NRS mean change from baseline; patients in the DS107 treatment groups (2g DS107 – 3.9 point reduction, 1g DS107 – 3.4 point reduction) achieved clinically meaningful and greater changes from baseline than placebo treated patients (2.3 point reduction).

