### 12.8.3 Secondary variables

IGA and EASI-75 responders at other time points will also be analysed using a GLMM model similar to that described in Section 12.8.2.

The efficacy variables and their changes from baseline will be summarized with descriptive statistics per treatment group and visit. This applies to the vIGA-AD™, EASI, NRS scores for pruritus, DLQI, POEM, SCORAD, AIS and PO-SCORAD. Change from baseline endpoints will be analysed using Mixed Model with Repeated Measures (MMRM) with Treatment Arm, Visit and Treatment x Visit Interaction as a factors and baseline value as a covariate, to account for missing data. The secondary efficacy analyses will be based on the FAS only. For vIGA-AD™ as a 5-level ordinal variable, mixed ordinal logistic regression will be used with factors defined as above and IGA at baseline as a factor too.

If rescue medication is used, the patient will be specified as a non-responder from the time the rescue is used

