## 2 Sample Size

In the Phase 2a trial, IGA response rates of 21.6% and 11.8% were observed for DS107 and placebo respectively resulting in a difference in response rates of 9.8%. Due to the prolonged treatment period of 16 weeks, a clinically relevant difference in IGA response rates of 15% was expected for the current study.

Assuming a placebo response rate of 12% and a true response rate difference of 15% at Week 16 and using a two-sided Chi-Square test on a significance of 5%, then 220 evaluable patients (110 patients per treatment arm) will be needed for 80% power to detect this difference as statistically significant. As the following table shows, the number of patients needed for the discovery of a 15% response rate difference depends also on the placebo response rate shown in the left column of the table as decimal numbers:

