**Number of patients per study group required under the assumptions as follows**  
**Chi-square test, 2 x 2 table, Two Proportions, two-sided.**  
**Sample Size 1 as a function of H1: Proportion 1 and Power.**  
**H1: Proportion 2 - Proportion 1=0,15 Significance Level=0,05 Sample Size 2 / Sample Size 1=1**

H1: Proportion 1 = Response Rate Placebo	Power		
	0,7	0,8	0,9
0,06	63,4	80,3	107,0
0,08	71,2	90,2	120,3
0,10	78,6	99,6	132,8
0,12	85,5	108,4	144,6
0,14	92,0	116,6	155,6
0,16	98,0	124,3	165,9
0,18	103,6	131,4	175,4
0,20	108,8	138,0	184,2

It was assumed that similar estimations apply to the primary endpoint EASI-75.

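### The change-score MMRM fits one baseline slope to all six visits and leaves the covariance structure unstated; adding baseline-by-visit may recover a modest amount of Week 16 precision

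*SAP*

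**What the plan says.** SAP 7.3 gives the MMRM for change scores "with Treatment Arm, Visit and Treatment x Visit Interaction as a factors and baseline value as a covariate, to account for missing data". The protocol body (12.8.3) matches: "Treatment Arm, Visit and Treatment x Visit Interaction as a factors and baseline value as a covariate". SAP 7.4 refers back to 7.3 for the exploratory change scores. The table list in SAP section 8 applies an MMRM to changes in vIGA-AD, EASI, worst itch NRS, BSA, SCORAD, DLQI, POEM, AIS and PO-SCORAD. Six post-baseline time points are modelled, for example "Change from baseline in EASI in treated population compared to placebo population to Week 4, 8, 12, 16, 18 and 20".

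The protocol synopsis describes a different model: "The models will include Treatment Arm as a factor and respective baseline value as a covariate, with the treatment-by-visit interaction term as a random effect". It has no baseline-by-visit term either.

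Neither document names a within-patient covariance structure. Neither gives an SD or a visit-to-visit correlation for any continuous score.

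**The concern.** Entering baseline once, as a main effect, forces the regression of change on baseline to be equal at all six visits. For change scores that is often untrue. As the correlation between baseline and the current score decays, the slope of change on baseline becomes more negative. The single fitted slope is then a compromise. If it is shallower than the true Week 16 slope, two things follow at Week 16:

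- Part of the variance that baseline could explain stays in the residual, so the interval is wider than necessary.
- A chance baseline imbalance between arms is only partly removed.

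What is at stake is precision on the continuous secondary and exploratory endpoints. Growth in mean improvement over time is not the issue, because the visit and treatment-by-visit terms already absorb it.

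**Working it through.** **1. The plan's own figure.** The only sizing is for the binary primary endpoint: "220 evaluable patients (110 patients per treatment arm) will be needed for 80% power". The inputs are 12% against 27%, two-sided 5%, so the mean rate is 0.195.

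n = [1.960 × √(2 × 0.195 × 0.805) + 0.842 × √(0.12 × 0.88 + 0.27 × 0.73)]² / 0.15² = (1.098 + 0.463)² / 0.0225 ≈ 108.3 per arm.

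The plan's table shows 108.4. Power at 110 per arm is 80.6%, so the figure reproduces. For EASI the plan adds only "It was assumed that similar estimations apply to the primary endpoint EASI-75", which concerns the responder rate. No precision figure for any MMRM endpoint exists to check, so everything below rests on assumed inputs.

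**2. Formulas (large sample).**
- Slope at visit t: b_t = cov(Y_t, Y_0)/var(Y_0) − 1.
- Common slope: β = (1′W⁻¹b)/(1′W⁻¹1), with W iterated to the fitted residual covariance.
- Proportional increase in Week 16 variance over the baseline-by-visit model: (b_16 − β)² × var(Y_0) / residual variance at Week 16.

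**3. Worked cases.** Total SD is constant and set to 1. The 4-week serial correlation is r, so b_4 = r − 1, b_16 = r⁴ − 1 and the Week 16 residual variance is 1 − r⁸. The fit is unstructured.

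| r | Week 4 slope | Week 16 slope | Common slope | Loss |
|---|---|---|---|---|
| 0.6 | −0.40 | −0.87 | −0.63 | 5.6% |
| 0.7 | −0.30 | −0.76 | −0.49 | 8.0% |
| 0.8 | −0.20 | −0.59 | −0.31 | 9.4% |
| 0.9 | −0.10 | −0.34 | −0.13 | 7.7% |

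For r = 0.8: (0.590 − 0.310)² / (1 − 0.8⁸) = 0.0784 / 0.832 = 9.4%. Here the residual SD after baseline rises from √(1 − 0.8²) = 0.60 at Week 4 to √0.832 = 0.91 at Week 16, although total SD is flat. That rise pulls the common slope toward the early visit.

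Now split the variance into a stable patient effect (0.3), a serial part (0.5, r = 0.8) and noise (0.2). The slopes are −0.30 at Week 4 and 0.3 + 0.5 × 0.8⁴ − 1 = −0.495 at Week 16, with a common slope of −0.393. The loss is 0.102² / (1 − 0.505²) = 0.0104 / 0.745 = 1.4%. If the data are compound-symmetric, the slopes are equal and the loss is zero.

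**4. Wider range.** There were 96 assumed settings: 8 variance mixes × 4 serial correlations (0.6-0.9) × 3 SD patterns (constant, up 30%, down 20% by Week 16). Position is 1 when the common slope equals the Week 4 value and 0 when it equals the Week 16 value.

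| Covariance fitted | Median loss | Range | Settings under 2% | Settings over 9% | Median position |
|---|---|---|---|---|---|
| Unstructured | 2.1% | 0-17.5% | 48% | 4% | 0.53 |
| Compound symmetry | 0.6% | 0-2.5% | 96% | 0% | 0.25 |
| AR(1) | 0.9% | 0-4.3% | 79% | 0% | 0.31 |

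The shares are illustrative, because the settings are assumptions.

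**5. Dependence on the residual SD.** Assume the slope steepens from −0.25 at Week 4 to −0.525 at Week 16 and is −0.475 at Week 20. Take baseline SD 8-12 and a residual correlation of 0.75 (exchangeable) or 0.85 (serial).
- Residual SD rising 7 to 10, unstructured fit: common slope about −0.21 to −0.27, loss about 4-14%.
- Constant residual SD, unstructured fit: about −0.38 to −0.43, loss about 1-4%.
- Residual SD falling 10 to 8, unstructured fit: about −0.44 to −0.56, loss about 0.1-1.5%.
- Compound symmetry fitted: about −0.43, loss about 0.6-2%.

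**6. Simulation.** With 220 patients, 1,200 runs per setting and an unstructured fit, the Week 16 variance ratio exceeded 1 by 0.8-9.7% with complete data and by 2.4-10.3% with 20% random dropout. The mean error in the Week 16 effect was never more than 0.004 baseline SD.

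**7. In patients.** A loss L equals 220 × (1 − 1/(1 + L)) patients: about 4 at 2% and about 18 at 9%. The interval widens by √1.02 − 1 = 1.0% and √1.09 − 1 = 4.4%.

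**The case against.** A single baseline covariate is a legitimate pre-specified choice. Randomisation protects the estimate, the only consequence is a slightly wide interval, and proof of efficacy rests on the two primary endpoints, which have their own GLMM (SAP 6.1). The loss also depends on quantities the plan does not state, so it may be negligible. The missing covariance structure and the conflicting synopsis are arguably the larger gaps. All of this stands, and it limits the point to a minor one. It does not argue for keeping the common slope, because the extra term costs almost nothing if the slopes turn out equal.

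Three stronger readings are tempting, and the documents do not support them.

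- **The common slope sits near its Week 4 value, and the loss is 2-9% in most plausible settings.** This needs an unstructured covariance and residual SD rising over time, and neither is stated. Otherwise the slope lies from about midway to at, or slightly past, the Week 16 value. Only about half of the unstructured settings above fall in 2-9%.
- **The trial's own premise contradicts a common slope.** The protocol says of the oral Phase 2b study that "The trend of improvement displayed no evidence of treatment plateau". That concerns response over time, not the regression of change on baseline. EASI-50 and EASI-75 are endpoint definitions, not claims of proportional improvement, and the itch responder endpoints are absolute reductions of 3 or 4 points.
- **The slope eases after treatment stops, at Weeks 18 and 20.** Protocol 1.6 reports higher response at the Week 10 follow-up than at Week 8: 50.0% against 41.7% for IGA on 2 g in the severe subgroup of the oral study, and 48.2% against 41.0% for EASI-75 on 5% cream.

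**Conclusion.** The point holds as a minor efficiency issue. As written, the MMRM has one baseline slope for six visits. If the true slopes differ, Week 16 change scores are under-adjusted and lose some precision: roughly 0-9% of variance, often under 2%, and more than 9% only in extreme settings. These figures are conditional on assumed SDs, correlations and covariance structures.

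A reader might infer bias or a threat to the primary result. Neither follows. The estimate is essentially unbiased under randomisation, and no bias was visible with complete data or with dropout unrelated to outcome. The primary endpoints do not use this model.

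**What to change.** Before unblinding, make one edit across the documents:

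- In SAP 7.3 (and so 7.4) and protocol 12.8.3, list the fixed effects as treatment, visit, treatment-by-visit, baseline value and baseline-by-visit. Take the treatment contrast at each scheduled week from that model.
- State the within-patient covariance structure in the same place, for example unstructured, with a named fallback if the model does not converge.
- Align the synopsis, which now makes treatment-by-visit a random effect, with the body.

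The cost is 5 degrees of freedom for a six-visit model (six slopes instead of one) with about 220 patients. No new data are needed and no endpoint changes. Adding the term after unblinding would look selective, so the timing matters.

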### 7.2 Inclusion Criteria

1. Patients with a clinically confirmed diagnosis of active AD according to the American Academy of Dermatology Consensus Criteria that has been present for at least 6 months before the screening visit.
2. Patients with moderate to severe AD at baseline as defined by a vIGA-ADTM score of 3 or 4 at baseline.
3. Patients with an EASI score of  $\geq 16$  at screening and baseline.
4. Patients with AD covering a minimum 10% of the body surface area (BSA) at baseline.
5. Patients with a worst itch NRS score in a day of  $\geq 4$  (on 11 point NRS) at the screening and baseline visits.
6. Patients whose pre-study clinical laboratory findings do not interfere with their participation in the study, in the opinion of the Investigator.
7. Patients who are able and willing to stop all current treatments for AD throughout the study (except for allowed emollients).
8. Patients who are on a stable dose of a bland emollient for at least 7 days prior to baseline.

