#### **4.2.6 Pruritus NRS**

Severity of pruritus related to AD will be self-assessed by patients daily using the NRS. Patients will be asked to estimate the intensity of pruritus at its worst over the previous 24 hours. The Pruritus NRS is a single-question assessment tool that will be used to assess the patient's worst itch as a result of AD in the previous 24 hours. Patients will score their pruritus due to AD on a scale of 0 – 10, with 0 (no itch) and 10 (worst itch imaginable) (Phan et al. 2012). Patients will complete the rating scale daily starting at screening through to the last study visit.

The baseline NRS is defined as the prorated average of the NRSs reported continuously for 7 days right before and on the baseline visit (i.e. study day -6 to day 1). For post-baseline NRS, the mean weekly worst itch NRS is calculated as the prorated average of the reported daily NRS within the week. For example, if there are 3 scores in a week, the prorated average = (score1 + score2 + score3)/3.

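### The 4-point itch responder endpoint can include patients whose 7-day mean baseline is below 4 and who therefore cannot respond; limit its main analysis to patients with a baseline of at least 4.

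*SAP*

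**What the plan says.** Three rules meet here.

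- **Entry (Protocol 7.2, criterion 5).** The wording is "Patients with a worst itch NRS score in a day of" at least 4, checked at the screening and baseline visits. No weekly mean is required.
- **Analysis baseline (SAP 4.2.6).** "The baseline NRS is defined as the prorated average of the NRSs reported continuously for 7 days right before and on the baseline visit", which the SAP gives as study days -6 to 1. After baseline, "the mean weekly worst itch NRS is calculated as the prorated average of the reported daily NRS within the week". The scale runs from 0 to 10.
- **Responder endpoints (SAP 7.3).** There are two: the "Absolute proportion of patients achieving a decrease of at least 4 points in worst itch NRS" and the "Absolute proportion of patients achieving a decrease of at least 3 points in worst itch NRS". For both, "The NRS endpoint should be recorded weekly (descriptive values), as defined in section 4.2.6".

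SAP 7.3 restricts the secondary efficacy analyses to the FAS. SAP section 3 and Protocol 12.6 define the FAS as everyone randomised and dosed, with no condition on itch. Tables 14.2.2.3.1, 14.2.2.3.2 and 14.2.2.3.7 in SAP section 8 also list the FAS.

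**The concern.** On a single-day scale the entry rule and the 4-point threshold fit together: a patient who enters with 4 or more can, in principle, fall by 4. The protocol's own description of the NRS (9.1.3) defines no weekly-mean baseline. SAP 4.2.6 introduces one, but neither the entry rule nor the denominator was adapted to it.

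Because the scale stops at 0, a patient's largest possible fall equals the baseline mean. Anyone with a mean below 4 is a certain non-responder on the 4-point endpoint. Such patients lower the rate in both arms and carry no information on whether DS107 relieves itch. What is at stake is how the reported proportion reads, with a small loss of power. The validity of the comparison is not at stake.

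**Working it through.** **1. How low the baseline can go.** Screening may be on any day from -14 to -1 (Protocol Appendix 1), so the screening score may or may not lie in the 7-day window.

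| Scores in the window | Baseline mean |
|---|---|
| Visit day 4, other six days 0 (screening outside the window) | 4/7 = 0.57 |
| Screening 4 and visit day 4, other five days 0 | 8/7 = 1.14 |
| Visit day 4, other six days 3 | (4 + 18)/7 = 3.14 |
| Screening the day before baseline, only two scores, both 4 | 8/2 = 4.00 |

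The third row is an ordinary pattern. That patient cannot fall by 4. A fall of 3 would need a weekly mean of 0.14 or less. The fourth row shows that the problem does not arise for every patient.

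**2. How many patients.** The documents give no baseline NRS distribution, so this step rests on assumptions. I simulated integer daily scores from 0 to 10, with a pre-selection mean of 5 to 7, a between-patient SD of 1.5 to 2 and a day-to-day SD of 1 to 2. A patient was eligible if both visit-day scores were at least 4. The screening day was placed outside the window.

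| Assumed mean | Weekly mean below 4 | Weekly mean below 3 |
|---|---|---|
| 5 | 6% to 9% | 0.4% to 1.9% |
| 6 | 2.4% to 4.4% | 0.1% to 0.8% |
| 7 | 0.7% to 2.0% | 0.02% to 0.3% |

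In 220 patients, 0.7% to 9% is about 2 to 20 (220 x 0.007 = 1.5; 220 x 0.09 = 19.8). For means below 3, it is 0 to about 4 (220 x 0.019 = 4.2).

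**3. Effect on the endpoint.** Let f be the share with a mean below 4. Each arm's 4-point rate p becomes (1 - f)p, so the difference becomes (1 - f)(p2 - p1).

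The plan has no power calculation for itch. Its only one is for IGA response, 12% against 27%, two-sided 5%, 80% power. It reproduces with n = [1.960 x sqrt(2 x 0.195 x 0.805) + 0.842 x sqrt(0.12 x 0.88 + 0.27 x 0.73)]^2 / 0.15^2 = 108.3 per arm (the SAP table has 108.4). With 110 per arm, power is 80.6%. I use the same test for itch with two assumed pairs of rates among patients able to respond. The restricted analysis has 110(1 - f) per arm.

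| Assumed rates | f | Difference in FAS | Power, FAS | Power, restricted |
|---|---|---|---|---|
| 12% vs 27% | 0 | 15.0 points | 80.6% | 80.6% |
| | 0.7% | 14.9 | 80.3% | 80.3% |
| | 5% | 14.3 | 78.0% | 78.6% |
| | 9.06% | 13.6 | 75.8% | 76.8% |
| 25% vs 40% | 0 | 15.0 | 66.3% | 66.3% |
| | 0.7% | 14.9 | 65.8% | 66.0% |
| | 5% | 14.3 | 63.0% | 64.0% |
| | 9.06% | 13.6 | 60.3% | 62.1% |

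Taken before rounding, restriction gains about 0.1 to 1.9 points of power. It recovers only part of the loss, because the number of patients also falls.

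**The case against.** The case for leaving the plan alone has five parts.

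- **The gain is small.** Restriction adds at most about 2 points of power. This stands, so the argument for change rests mainly on interpretation.
- **The protocol's endpoint is a proportion of patients.** Restricting the denominator departs from that. This stands in part, and is why the full-FAS proportion should be kept as supportive.
- **Itch is covered elsewhere.** The change-from-baseline NRS analysis, with baseline as covariate, uses everyone, and the 3-point endpoint can still count patients with means between 3 and 4. This is true, but it does not alter what the 4-point proportion reports.
- **The baseline might not be fully pre-dose.** The window ends on study day 1, which SAP 4.2.1 defines as the date of first treatment. Nothing says that the day-1 diary score precedes the dose. This stands, and the fix must deal with it.
- **SAP 4.1.4 gives a different general baseline**, the last non-missing value before treatment. That does not remove the mismatch, because 4.2.6 defines the NRS baseline specifically and 7.3 points to 4.2.6.

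A reader might also infer more than the documents support:

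- That both itch responder endpoints are materially diluted. For the 3-point endpoint the mean must be below 3, which the entry rule allows but which affects only about 0.02% to 1.9% in the simulation.
- That patients with baselines from 4.0 to 4.9 belong to the problem. They can respond, and they would stay in the denominator.
- That the treatment comparison is biased. Randomisation places these patients in both arms, and a comparison with no true effect stays valid.

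**Conclusion.** The mismatch holds on the text: the plan admits patients who cannot meet the 4-point criterion and keeps them in its denominator. The documents show that such patients can be enrolled, not how many will be. The 0.7% to 9% range depends on the assumed itch distributions, and the top of it needs the lowest mean and the largest day-to-day variation considered. If 9.06% are affected, an assumed 15-point difference falls to 13.6 points; if 0.7%, to 14.9.

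This concerns one secondary endpoint, with a minor consistency point for a second. The sample size and the two primary endpoints, on which success is judged, are untouched. The change is worth making because it costs almost nothing, removes patients whose result is settled before treatment, and lowers power in none of the settings calculated.

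**What to change.** In SAP 7.3 and tables 14.2.2.3.1 and 14.2.2.3.7:

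1. Make the main analysis of the 4-point endpoint the FAS patients with a weekly mean baseline NRS of at least 4.
2. Compute that baseline only from scores recorded before the first dose, so that the subset is defined before treatment and the randomised comparison is kept. State that 4.2.6, not 4.1.4, governs the NRS baseline.
3. Report the full-FAS 4-point proportion as supportive.
4. Optionally, for consistency, use a baseline of at least 3 for the 3-point endpoint (table 14.2.2.3.2 and its part of 14.2.2.3.7). Little will change.
5. Leave the change-from-baseline NRS analysis in the full FAS.

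The cost is a short SAP addition and a slightly smaller denominator on a secondary endpoint. It should be written before unblinding, because a denominator chosen later would look data-driven.
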